5.2. Schematic study design

Screening assessments are performed subsequent to the patient providing an informed consent and within 28 days before the first administration of SL-901 at the Run-in PK sampling day, unless otherwise specified.

In both study parts a treatment cycle is considered to be 28 days, with daily dosing throughout the cycle.

All patients will receive SL-901 as a single agent in an open-label fashion; study drug will be dispensed to patients at scheduled study center visits on a per-cycle basis. SL-901 capsules (20 mg and 60 mg) are packaged into 50-cc high-density polyethylene (HDPE) bottles, 14 capsules per bottle.

Tumor assessment will occur at Screening (for identification of baseline disease) and every 2 cycles of treatment thereafter. Response will be evaluated using Response Evaluation Criteria in Solid Tumors (RECIST) v1.1.

[figure not shown]
In Part 1a, a serially sampled PK profile will be obtained for a single dose (Run-in PK sampling) and at steady-state (C1D15); in Part 1b, the PK sample collection schedule will be informed by data collected in Part 1a.

[figure not shown]
All Serious Adverse Events (SAEs) and non-SAEs will be recorded in the study's clinical database from the day of informed consent signature (SAEs) or from the day of first exposure to SL-901 (AEs) through 30 days after the last dose of SL-901.

[figure not shown]
After completion of the End of Treatment (EOT) visit, patients will then be followed every 90 days for survival status for 12 months. The survival follow-up may be by telephone contact. If the patient discontinued study drug for reasons other than progressive disease, disease assessments should continue to be performed on an every 8-week basis (± 1 week) through 6 months after the first study drug dose and then on an every 90-day basis or until, in the judgment of the Investigator, there is evidence of relapsed or progressive disease.

[figure not shown]
5.3. Study flow chart

The schedule of assessments for the study is provided in Table 2 (Screening period, Run-in pharmacokinetic [PK] and Cycles 1-2) and Table 3 (Cycle 3 and beyond). PK assessment schedule is provided in Table 4.

5.4. Study Endpoints

5.4.1. Primary endpoints

- Safety endpoints include
 - identification of DLTs;
 - rate of treatment-emergent adverse events (TEAEs) and SAEs;
 - identification of abnormalities in physical examination, vital signs, clinical laboratory evaluations;
 - ECG findings.
- PK endpoints include
 - assessment of SL-901 plasma concentration over time;
 - assessment of any changes in the PK properties of SL-901 between initial administration and steady-state and between cycles of treatment;
 - explore the correlation between PK parameters and toxicity.

5.4.2. Secondary endpoints

- PD assessment of target phosphorylation will be performed using a PI3K pathway triple assay (p-AKT, p-p70S6K, and p-GSK3) in platelet-rich plasma and/or tumor tissue and using immunofluorescence for gamma H2AX in PBMCs.

- Clinical activity endpoints include
 - Objective Response Rate (ORR);
 - Disease Control Rate (DCR)
 - Complete Response Rate (CRR);
 - Duration of Response (DOR);
 - Duration of Complete Response (DOCR)
 - Progression-free survival (PFS);
 - Overall Survival (OS).

5.4.3. Exploratory endpoints

Not applicable.

5.4.4. Safety endpoints

The Safety endpoints are included among the planned primary endpoints. Please refer to paragraph 5.4.1.

6. General specifications

6.1. Data validation

Medidata Classic Rave ® 2020.3. 2 and following software release will be used as Electronic Data Capture (EDC) system for data entry, by site personnel and for data cleaning and data locking by the Menarini Ricerche Data Management team.

The eCRF data are elaborated to create the SDTM (v1.8) and ADaM (v2.1) CDISC standard datasets.

6.2. Computer system and software used

The software used for all summary statistics and statistical analyses will be SAS Studio ® 9.04.01 or higher (SAS Institute, Inc.). All tables and listings will be produced using PROC REPORT or procedure specific output displays using output delivery system (ODS). The summary tables and listings will use SAS monospace font of size 6. The default page type will be A4 and the default page orientation will be landscape.

The PK parameters will be determined from the individual plasma concentration time curves using non-compartmental methods with Phoenix™ WinNonlin® software, version 6.4 or higher (Pharsight Corp., Mountain View, California).

6.3. Coding systems

6.3.1. Clinical Terms

Concomitant diseases, medical procedures, and Adverse Events will be coded with MedDRA version 23.1 or subsequent versions.

6.3.2. Drugs

Drugs will be coded with WHO (ATC coding system) Drug version Mar-2021 or subsequent versions.

6.3.3. Classification criteria

Adverse Events will be graded for severity using the classifications of Common Terminology Criteria for Adverse Events (CTCAE) Version 5.0 (November 27, 2017).

6.4. Report type, language, format

The statistical output will be in word and .pdf format and in English language.

Dates will be presented with the DDMMYY format.

Counts and percentages:

<group 1> xxx (xx.xx%)

Counts and percentages including also the count of the event of interest will be displayed in two separated columns:

	n (%)	No. of events
	xx (xx.xx %)	xxx

Descriptive statistics:	n	xxx
	Mean	xxx.xx
	Median	xxx.xx
	SD	xxx.xxx
	Minimum	same precision as individual value
	Maximum	same precision as individual value

In general, the following rule will be applied for decimal place:

- o Minimum, maximum: one decimal place
- o Arithmetic mean and median: one more decimal than minimum/maximum

- o SD: one more decimal than arithmetic mean/median
- o N: no decimal places

Character values will be left aligned.

Numeric values will be decimal-point aligned.

6.5. Standard Operating Procedures (SOPs) to be followed

¹ Code	Title
MR-GCS-DMST-210_SOP	Statistical Analysis Plan (SAP)
MR-GCS-DMST-211_SOP	Statistical Programs Writing
MR-GCS-DMST-211.3_WI	TLF programming
MR-GCS-CP&P-504	Use and management of Phoenix® WinNonlin® and pharmacokinetic data flow
MR-GCS-CP&P-505	Standard methods for non-compartmental analysis of pharmacokinetic data

6.6. Data Transfer Agreements

Data not directly entered in eCRF like (and not limited to):

- PK concentrations – [REDACTED] “STML_901_0119_PK_Concentrations_DTA V1.0”
- PK analysis results – Clinical Pharmacology and Pharmacometrics team Menarini Ricerche S.p.A
“STML_901_0119_PK_DTA V1.0”
- PD results - [REDACTED]

are transferred to the Sponsor based on specific Data Transfer Agreements (DTA).

For the details regarding DTAs and the management of the received data, please refer to the Clinical Data Management Plan.

7. Definitions and general methodology

7.1. Data quality assurance

All tables, figures and data listings to be included in the report will be independently checked for consistency, integrity and in accordance with Menarini Ricerche standard procedures.

7.2. General considerations and key definitions

7.2.1. General considerations

Study day is defined as the number of days from the date of first dose of SL-901 to the event/visit date. For dates equal to or later than the first dose of study drug, study day is calculated as follows:

Study Day = Event or Visit Date – First Dose Date + 1

For dates prior to the first dose of study drug, study day is calculated as follows:

Study Day = Event or Visit Date – First Dose Date

One (1) month will be considered to be equal to 30.4375 days when calculating durations or survival times in months.

7.2.2. Key definitions

Baseline

Baseline is defined as the last non-missing assessment prior to the date and time of the first SL-901 dose.

Change from Baseline

Change from Baseline (absolute value) = post-baseline value – baseline value.

Adverse Events (AEs)

An AE is any untoward medical occurrence in a study patient who is administered a medicinal product (study drug), regardless whether or not considered drug-related. An AE can therefore be any unfavorable and unintended sign including abnormal laboratory/examination findings, symptoms, or disease(s) temporally associated with the use of study drug, whether or not related to study drug. An AE can arise from any use of the drug (e.g., off-label use, use in combination with another drug) and from any route of administration, formulation, or dose, including an overdose.

Treatment-Emergent Adverse Events (TEAEs)

If an Adverse Event occurs for the first time or if it worsens in terms of grade, seriousness or severity on or after the first on or after the date and time of the first dose of SL-901 and up to 30 days after the last dose of SL-901, it will be classified as TEAE, otherwise it will be classified as non-TEAE. Where an AE date is partial or missing, and it is unclear whether the AE is treatment-emergent, the AE will be assumed to be treatment-emergent.

Adverse Drug Reactions (ADRs)

Untoward and unintended responses to an Investigational Medicinal Product (IMP) related to any dose administered. The definition also covers medication errors and uses outside what is foreseen in the protocol, including misuse and abuse of the product. The definition implies a 'reasonable possibility of a causal relationship between the event and the IMP. This means that there are facts (evidence) or arguments to suggest a causal relationship.

All AEs (including SAEs) are to be accurately recorded on the AE page of the patient's electronic case report form (eCRF). Each event will be graded for severity using the classifications of NCI CTCAE (see section 6.3.3).

- **Grade 1 / Mild** - AE that disappears or is easily tolerated on continuation of study drug;
- **Grade 2 / Moderate** – AE that disappears or is easily tolerated on continuation of study drug;
- **Grade 3 / Severe** - AE sufficiently discomforting to cause interference with usual work activities;
- **Grade 4 / Life-threatening** - AE that is potentially life-threatening.
- **Grade 5 / Fatal** - Results in the patient's death.

A severe event is not necessarily a serious event. For example, a headache may be severe (interferes significantly with patient's usual function) but would not be classified as serious unless it met one of the criteria for serious events as defined below.

Serious Adverse Event (SAE) / Serious Adverse Drug Reaction (SADR)

Any untoward medical occurrence or effect that at any dose:

- Results in death.

- Is life-threatening. Life-threatening means that the patient was at immediate risk of death from the reaction as it occurred (i.e., it does not include a reaction which hypothetically might have caused death had it occurred in a more severe form).
- Requires in-patient hospitalization or prolongation of existing hospitalization. Hospitalization admissions and/or surgical operations scheduled to occur during the study period, but planned before study entry are not considered adverse events if the illness or disease existed before the patient was enrolled in the study, provided that it did not deteriorate in an unexpected manner during the study (e.g. surgery performed earlier than planned).
- Results in persistent or significant disability/incapacity or substantial disruption of
- the ability to conduct normal life functions.
- Results in a congenital anomaly/birth defect

Any other AE/ADR which is not included in the above definitions will be considered as non-serious. The Investigator should also promptly report all the SAEs to the Sponsor's Drug Safety Manager.

Algorithm for Causality Assessment of Adverse Events

The causality (causal relationship to the study drug) of AEs will be assessed based on the following algorithm:

1. **Definitely related:** An AE, including a laboratory test abnormality assessed as clinically significant (CS), is considered certainly related to a drug when it occurs in a plausible time relation to the administration of the drug, and which cannot be explained by concurrent disease or other drugs or chemicals. The response to withdrawal of the drug (de-challenge) should be clinically plausible. The event must be definitely related, pharmacologically or phenomenologically, using a satisfactory re-challenge procedure if necessary.
2. **Probably related:** An AE, including a laboratory test abnormality assessed as CS, is considered probably related to a drug when it occurs in a reasonable time relation to the administration of the drug, is unlikely to be attributed to concurrent disease or other drugs or chemicals, and which follows a clinically reasonable response on withdrawal (de-challenge). Re-challenge information (AE reappearance after drug reintroduction) is not required to fulfil this definition.
3. **Possibly related:** An AE, including a laboratory test abnormality assessed as CS, is considered possibly related to a drug when it occurs in a reasonable time relation to the administration of the drug, or it could also be explained by concurrent disease or other drugs or chemicals. Information on drug withdrawal (de-challenge) may be lacking or unclear.

4. **Unlikely related:** An AE, including a laboratory test abnormality assessed as CS, is considered unlikely related to a drug when other drugs, chemicals or underlying disease provide plausible explanations and/or the temporal relation to the administration of the drug makes a causal relation improbable.
5. **Unrelated:** An AE, including a laboratory test abnormality assessed as CS, is considered not related to the use of a drug in case of existence of a clear alternative explanation and/or unreasonable temporal relationship, and/or non plausibility.

An AE in which the relationship is ranked 1, 2, 3 is defined as an ADR. AEs ranked 4 or 5 are not considered as ADRs.

7.3. Analysis populations

The following analysis populations will be considered in the statistical analysis:

- DLT population: All patients receiving the complete run-in dose and at least 75% of the planned SL-901 doses in Cycle 1 and completing study assessments through C2D1, or patients discontinuing Cycle 1 due to DLT irrespective of the SL-901 dose actually received.
- Safety population: all patients enrolled into the study and who received any amount of SL-901.
- Efficacy population: all patients enrolled into the study and who received any amount of SL-901 (it corresponds to the safety population).
- Per Protocol (PP) population: all patients who received at least 1 cycle of treatment, have at least 1 post-baseline efficacy assessment, and have no major protocol violations.
- PK population: all patients who receive at least one dose of SL-901 and have at least one PK sample collected and the corresponding PK concentration. .

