6.4.2. Dose-Limiting Toxicities

Patients are to receive at least 75% of the planned SL-901 doses in C1 and complete study assessments through C2D1 to be eligible for DLT evaluation, unless discontinuing due to DLT. Patients who receive <75% of the planned SL-901 doses in C1 and/or discontinue before completing study assessments through C2D1 for reasons other than DLT are to be replaced.

Toxicities are to be assessed by the Investigator according the NCI CTCAE, v5.0 (available at:

https://ctep.cancer.gov/protocoldevelopment/electronic_applications/docs/CTCAE_v5_Quick_Reference_5x7.pdf.

A DLT occurring during the Run-in PK period or in C1 is defined as any of the following AEs for which there is a reasonable possibility that SL-901 caused the event. (Note that while causality of an AE is to be determined by the Investigator, the Sponsor's assessment of causality can be used to override an Investigator's designation of 'unrelated'; however, the Sponsor's assessment cannot be used to reverse an Investigator's designation of 'related' for the purpose of DLT determination.

- Any \geq Grade 3 non-hematologic AEs, with the exceptions of:
 - Grade 3 nausea, vomiting, diarrhea, constipation, fever, fatigue, or skin rash that resolves to Grade <3 within 72 hours.
 - Grade 3 laboratory abnormalities that are not associated with symptoms and resolve to Grade 1 or baseline by C1D28 (unless otherwise specified).
- Grade 4 thrombocytopenia or Grade 3 thrombocytopenia with $>$ Grade 1 bleeding or requirement for platelet transfusion.
- Grade 4 neutropenia lasting >5 days.
- Febrile neutropenia (ANC $<1\times10^9/L$ with fever $\geq38.5^{\circ}\text{C}$) of any duration.
- Persistent anemia (i.e., lasting >96 hours despite >2 red blood cell [RBC] transfusions).
- \geq Grade 3 transaminase (AST/ ALT) elevation.
- Any toxicity resulting in >7 held/skipped doses.
- Any other significant toxicity considered by the Investigator or the Sponsor to be dose-limiting (e.g., any toxicity considered at least possibly related to SL-901 that results in patient withdrawal during C1).

In situations in which DLTs have occurred that would prevent further dose-escalation and are severe but not life-threatening (i.e., persistent Grade 3 fever, malaise), re-evaluation of specific dose cohorts may be considered with co-administration of appropriate supportive care agents (e.g., corticosteroids, anti-depressants) concomitant with SL-901 therapy.

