6.5. Rationale for the Dose(s) Selected

6.6. Dose Interruptions and Reductions

For patients that develop a clinically significant AE or unacceptable toxicity during treatment, dosing should be interrupted.

- If the toxicity resolves to the baseline level or Grade 1 within 7 days, then dosing should resume at the same dose level (during C2 and beyond, dose reduction may also be considered in consultation with the Sponsor).
- If the toxicity resolves to the baseline level or Grade 1 within 8 to 14 days, then dosing in C2 and beyond may be resumed at a reduced dose after consultation with the Sponsor.
- If the toxicity fails to resolve to baseline or Grade 1 within 14 days, then the patient should be discontinued from treatment permanently.

Specific management of unusual non-autoimmune and non-infectious toxicities known to be associated with PI3K inhibitors are summarized in [Table 6 \(Greenwell 2017\)](#).

Table 6: Management of Unusual Non-Autoimmune and Non-Infectious Toxicities

	Hypertension	Hyperglycemia	Confusion	Anxiety/ depression	Rash
Observe	BP \geq 140/90 mmHg	FG ULN-160 mg/dL	Mild disorientation	Mild symptoms	\leq 30% BSA
Hold Drug	BP \geq 200/110 mmHg	FG $>$ 160 mg/dL or NFG \geq 200 mg/dL	Limit ADL	Limit ADL	$>$ 30% BSA

Abbreviations: ADL = activities of daily living, BP = blood pressure, BSA = body surface area, FG = fasting glucose, NFG = non fasting glucose, ULN = upper limit of normal

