7.3. Treatment Discontinuation

Study drug may be discontinued for any of the following reasons:

- Progression of disease that, in the opinion of the Investigator, precludes further study treatment. After consultation with the Sponsor, SL-901 may be continued for a patient who has met the criteria for progressive disease but in the Investigator's opinion, continues to derive benefit from study treatment.
- Occurrence of an unacceptable AE, including DLT.
- Pregnancy.
- SL-901 interruption due to study drug-related toxicity for >1 cycle (i.e., >28 days). Interruptions or delays >28 days for reasons other than AEs and/or in the setting of sustained disease control may be acceptable and are to be discussed with the Medical Monitor.
- Patient requires use of a prohibited concomitant medication or therapy.
- General or specific changes in the patient's condition unacceptable for further treatment within the study parameters, in the judgment of the Investigator.
- Non-compliance.

- Lost to follow-up.
- Patient withdrawal of consent.
- Sponsor request.
- Other.

All study procedures outlined for the End-of-Treatment (EOT) visit should be performed 30 days (± 3 days) after the last study drug dose.

In Part 1a, patients who receive <75% of the planned SL-901 doses in C1 and/or discontinue from the study before completing study assessments through C2D1 for reasons other than DLT are to be replaced.

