8.8. Pharmacokinetics

See [Table 8](#) for the PK assessment schedule.

A large black rectangular box redacting content from the original document.

8.9. **Electrocardiogram**

Twelve-lead ECGs will be performed 5 to 10 minutes before the PK sample is collected and analyzed locally in triplicate over 5 minutes (\pm 5 minutes) contemporaneously with selected PK sampling time points, as indicated in [Table 8](#).

Table 8: Time Points for Pharmacokinetic and Electrocardiogram Assessments

Timepoint	Run-in Serial PK Sampling and ECGs (3-7 days before C1D1; Part 1a only)		Steady State Sampling and ECGs (C1D8; C1D22; C2D1; C2D8; C2D15; C2D22; Cycles 3 and beyond D1, D15 Part 1a and Part 1b)		Serial PK Sampling and ECGs (C1D15 Part 1a and Part 1b)	
	PK	ECG¹	PK	ECG¹	PK	ECG¹
Predose	X	X	X	X	X	X
60 minutes postdose	X	X	--	--	X	X
2 hours postdose	X	X	--	--	X	X
4 hours postdose	X	X	--	--	X	--
6 hours postdose	X	--	--	--	X	--
8 hours postdose	X	--	--	--	X	--
10 hours postdose	X	--	--	--	X	--
12 hours postdose	X	--	--	--	X	--
24 hours postdose	X	X	--	--	X	X
48 hours postdose	X	X	--	--	--	--
72 hours postdose	X	X	--	--	--	--

C = cycle, D = day, ECG = electrocardiogram, PK = pharmacokinetic

¹. ECG should be performed as triplicates and at least 5-10 minutes before the PK sample is collected.

8.10. **Pharmacodynamics**

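### The SAP 7.3 exception for DLT patients is narrower than the SAP's own DLT window: a patient with a run-in DLT, or one with a DLT who stays on treatment, can fall outside the DLT population

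*SAP*

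**What the plan says.** **The population.** SAP 7.3 admits a patient to the DLT population in either of two ways.

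- Limb 1: the complete run-in dose, 75% or more of the planned Cycle 1 doses, and assessments through C2D1.
- Limb 2: "or patients discontinuing Cycle 1 due to DLT irrespective of the SL-901 dose actually received".

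SAP 3.1 records one change from the protocol here. Because the run-in belongs to the DLT assessment period, the full run-in dose was added to the conditions.

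**The protocol's version.** Protocol 6.4.2 sets the 75% and C2D1 conditions for a patient "to be eligible for DLT evaluation, unless discontinuing due to DLT". It does not name Cycle 1 in that exemption.

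**The window and the MTD.** SAP 5.1 and Protocol 6.4.2 both count DLTs from the run-in PK period as well as Cycle 1. SAP 5.1 defines the MTD by how many subjects experience a DLT in that window, with no condition on discontinuation. Protocol Table 8 places the run-in "3-7 days before C1D1; Part 1a only".

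**What follows a toxicity.** Protocol 6.6 says that if toxicity resolves "within 7 days, then dosing should resume at the same dose level". If it resolves "within 8 to 14 days, then dosing in C2 and beyond may be resumed at a reduced dose". Protocol 7.3 opens its list, which includes a DLT, with "Study drug may be discontinued for any of the following reasons".

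**Use.** SAP 11.5.1 presents DLTs on the DLT population. The table is 14.3.1.1.2.

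**The concern.** Whether a patient has had a DLT and whether that patient stopped Cycle 1 are different facts. The window and the MTD definition use the first; the exception in SAP 7.3 uses the second. SAP 3.1 extended limb 1 to the run-in but left limb 2 tied to Cycle 1.

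Identification of DLTs is a primary endpoint (SAP 5.4.1). A DLT patient in neither limb would drop out of the table that reports it, from numerator and denominator together. That can only lower the reported proportion or leave it unchanged. The table could then disagree with the count of subjects on which SAP 5.1 bases the MTD. With 3 to 6 patients per cohort, one patient is enough to show.

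**Working it through.** **The plan's own figure.** SAP 8 and Protocol 9.1 call 33% the marginal DLT rate for expanding from 3 to 6 patients: 1/3 = 33.3%. It is reproduced and not in dispute.

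**Inputs.** A cycle is 28 days with daily dosing (Protocol 6.4), so Cycle 1 has 28 planned doses on QD and 2 × 28 = 56 on BID. The 75% condition requires 0.75 × 28 = 21 doses (at most 7 missed) or 0.75 × 56 = 42 doses (at most 14 missed).

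**Patient (i): run-in DLT, Cycle 1 never started.** The run-in dose comes before C1D1, and its toxicity is inside the window.

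- Limb 1: 0/28 or 0/56 = 0%, so it fails.
- Limb 2: there is no Cycle 1 to discontinue, so it fails as worded.
- Protocol 6.4.2: a patient who stops for a DLT is exempt whatever the period, so the patient is covered.

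This gap therefore exists only in the SAP.

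**Patient (ii): DLT, treatment not discontinued, a limb 1 condition failed.** Take a DLT that qualifies on grade, such as "Grade 3 transaminase (AST/ ALT) elevation" (the protocol's threshold is that grade or higher). The drug is held, the toxicity resolves within 7 days, and dosing resumes under Protocol 6.6.

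| Cycle 1 doses missed | QD received | BID received | 75% met? |
|---|---|---|---|
| 7-day hold only | 21/28 = 75.0% | 42/56 = 75.0% | yes |
| 7-day hold + 1 further dose | 20/28 = 71.4% | 41/56 = 73.2% | no |

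In the second row the patient has a DLT, is still on treatment, and is in neither limb. The same holds for a DLT patient who stays on drug but misses the C2D1 assessments. Protocol 6.4.2 also exempts only those who discontinue, so the protocol shares this gap.

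**The held-dose criterion.** The list also includes "Any toxicity resulting in >7 held/skipped doses".

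- On BID, a 7-day hold is already 14 held doses, so the criterion is met. One further missed dose gives 41/56 = 73.2%.
- On QD, 8 held doses give 20/28 = 71.4%. If these come from separate shorter holds, the criterion is met only if doses are added up for one toxicity, which is not stated. If they come from one unbroken hold of 8 to 14 days, Protocol 6.6 gives a route back only from Cycle 2, and that may count as discontinuing Cycle 1.

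**Effect on the table.** Leaving out one DLT patient turns x/n into (x − 1)/(n − 1). The difference is x/n − (x − 1)/(n − 1) = (n − x)/[n(n − 1)], which is never negative and is zero only when x = n. With one affected patient who is not replaced:

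| Patients with a DLT | Shown in Table 14.3.1.1.2 |
|---|---|
| 2/6 = 33.3% | 1/5 = 20.0% |
| 1/6 = 16.7% | 0/5 = 0% |
| 2/3 = 66.7% | 1/2 = 50.0% |
| 3/3 = 100% | 2/2 = 100% |

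These counts are illustrations; the documents give no results. If the omitted patient in the first row were replaced by one without a DLT, the table would show 1/6 = 16.7%, against 2/7 = 28.6% of those treated.

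**The case against.** The best defence is intent. Limb 2 waives the dose condition, SAP 3.1 was written because the run-in counts, and the replacement sentence in SAP 5.1 exempts discontinuation for a DLT without naming Cycle 1. Together these suggest that DLT patients were meant to be kept. I accept that: this is a drafting gap, not a decision to drop anyone. But a population flag is programmed from the written definition, and the data review meeting in SAP 7.4.2 is described as settling only Per Protocol membership.

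Other limits also stand.

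- Patient (ii) is narrow. One unbroken hold of up to 7 days passes 75% on either schedule.
- A reader might infer that every QD patient with the held-dose DLT is excluded. The documents do not support that, because of the unstated counting rule and the possible reading of an 8 to 14 day hold given above.
- The permissive opening of Protocol 7.3 is weak evidence that stopping is optional: the same list includes pregnancy, where Protocol 8.1.3 and 8.6 require discontinuation. The argument rests on Protocol 6.6 instead.
- An incomplete run-in dose is a remote route to exclusion, since Protocol 6.4 has the drug given at the study center on PK days.
- The replacement sentences can be read literally as replacing any patient below 75%, so the 1/5 and 0/5 figures hold only without replacement.
- The event would remain in the Safety-population TEAE tables and the all-AE listing. Table 14.1.1.1 and Listing 16.2.1.2 would show who is in each population.

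**Conclusion.** The point holds as a wording defect of minor severity. SAP 7.3's exception is narrower than the window and MTD definition in SAP 5.1. Gap (i) is new in the SAP; gap (ii) is shared with Protocol 6.4.2. A reader might assume that the protocol has both gaps, but its exemption is not tied to Cycle 1.

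For one affected, unreplaced patient, 2/6 (33.3%) would show as 1/5 (20.0%), or 1/6 (16.7%) as 0/5. This assumes a literal reading of SAP 7.3 and that such a patient exists. The documents do not say how many there were; it may be none.

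A reader might also infer that an MTD or an escalation step was wrong. The documents do not support that. Protocol 6.4.1 counts patients who experience a DLT, a review committee decided each step, and SAP 4 states that the study stopped early with Part 1b not started. The consequence is confined to one descriptive table, although that table reports a primary endpoint.

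**What to change.** In SAP 7.3, define the DLT population as:

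- (a) every treated patient with a DLT in the run-in PK period or Cycle 1, whatever the dose received, the assessments completed, or whether treatment was discontinued; plus
- (b) patients without a DLT who received the full run-in dose and 75% or more of Cycle 1 doses and completed assessments through C2D1.

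In SAP 3.1, record only the inclusion of DLT patients who do not discontinue as a change from Protocol 6.4.2. Covering the run-in discontinuation restores the protocol's own exemption.

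The replacement sentences in SAP 5.1 and in Protocol 6.4.2 and 7.3 should be reconciled with this set. No replacement or dosing rule is proposed here.

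The cost is one sentence in SAP 7.3, one line in SAP 3.1 and that reconciliation. It needs no extra patients or data. It should be settled before database lock, when SAP 3 has the plan finalized.
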